12.2.3 Safety Analysis Set

The SafAS is defined as those subjects who have received at least one dose of the study vaccines. All subjects will have their safety analyzed after each dose according to the vaccine they actually received, and after any dose according to the vaccine received at first dose. The safety data will also be presented separately for dengue-exposed and dengue unexposed subjects.

Safety data recorded for a vaccine received out of the protocol design will be excluded from the analysis (and listed separately).

Note: Subjects will be included in the “any dose” analysis according to the 1st dose received that correspond to a protocol group.

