## 3 Description of the Overall Trial Design and Plan

### 3.1 Trial Design

This is a Phase IIIb, randomized, open-label, multicenter study in 480 healthy female subjects aged 9 to 14 years in Mexico.

Subjects were to be randomized in a 1:1 ratio into one of the 2 following groups to receive:

- Group 1 (N=240): 3 doses of CYD dengue vaccine and 2 doses of Cervarix (Human Papillomavirus Bivalent [Types 16 and 18] Vaccine, Recombinant; GlaxoSmithKline) concomitantly to the 2 first doses of CYD dengue vaccine
- Group 2 (N=240): 3 doses of CYD dengue vaccine and 2 doses of Cervarix sequentially to the 2 first doses of CYD dengue vaccine

For both vaccines, each dose is to be administered 6 months apart.

As per Protocol Amendment 1, only subjects identified as dengue immune (seropositive) before administration of the first CYD dengue injection (at V01 for Group 1 and at V02 for Group 2) and who consented to receive the remaining injection of dengue vaccine could remain in the study as per initial study procedures.

Subjects identified as non-immune (seronegative) at baseline could continue in the study for a 6-month safety follow-up. They did not receive the third and last injection of the CYD dengue vaccine.

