##### ***Safety***

All analyses will be descriptive; no hypotheses will be tested. Safety will be assessed for all subjects and for immune subjects after each and any dose of Cervarix and CYD Dengue vaccine. Moreover, a complementary analysis will be performed for each dose of CYD dengue vaccine, for each and any group, on non-immune subjects.

As there are differences in the intensity considered for measurable reactions depending on ages of subjects, a complementary analysis will be performed according to the following age groups: 9-11 years and 12 to 14 years.

For the main parameters, 95% CIs of point estimates will be calculated using the normal approximation for quantitative data and the exact binomial distribution (Clopper-Pearson method, quoted by Newcombe) for single proportions.

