#### **5.2.3 Safety Analysis Set**

The SafAS is defined as those subjects who have received at least one dose of the study vaccines. All subjects will have their safety analyzed after each dose according to the vaccine they actually received, and after any dose according to the vaccine received at first dose. The safety data will also be presented separately for dengue immune, non-immune / undetermined subjects.

Safety data recorded for a vaccine received out of the protocol design will be excluded from the analysis (and listed separately).

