## 5.2.5 Populations Used in Analyses

The main immunogenicity analyses (non-inferiority tests) will be performed on the per protocol analyses sets PPX and PPC respectively for Cervarix and CYD dengue vaccine comparisons. The subjects will be analyzed by the vaccine group to which they were randomized.

All other immunogenicity analyses will be performed on the FAS and by baseline dengue status. Subjects will be analyzed by the vaccine group to which they were randomized.

The safety analyses will be performed on the SafAS. Subjects will be analyzed according to the vaccine they actually received and by baseline dengue status.

Complementary analyses on Zika and FV baseline statuses (and by baseline dengue status) will be performed on randomized subjects and on the FAS.

Dengue GMTs by Zika and by FV baseline statuses by Zika baseline status will be performed on all subjects and on FAS dengue immune subjects.

Description of immune response to each dengue serotype according to Zika status at baseline will be performed on FAS dengue immune subjects.

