## 5.7 Changes in the Conduct of the Trial or Planned Analyses

According to Protocol amendment 1, the study population for the non-inferiority is reduced to the dengue immune subjects (seropositive) compared to initial sample size.

The full analysis set for dengue immune (seropositive) subjects population described in the protocol is no more useful because results for immunogenicity and safety will be presented by baseline dengue status.

To further assess the potential impact of prior infection by zika on the immune response induced by the CYD dengue vaccine and on dengue injection, an exploratory analysis will be performed on subjects who have accepted further testing on their BS in the ICF. Description will be done according to Zika and FV baseline status and on dengue characteristic according to the Zika and FV baseline status.

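### Any-dose safety percentages are not comparable across baseline dengue status, because CYD dose 3 continued only in immune girls, and the SAP is inconsistent on whether such tables are planned

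*SAP*

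**What the plan says.** Since Protocol Amendment 1, exposure to CYD depends on baseline dengue status. Immune girls who consented could receive dose 3. Of non-immune girls, SAP section 3.1 says: "They did not receive the third and last injection of the CYD dengue vaccine". Protocol section 1.4 records that, when the study was paused, every subject had already had two injections of each vaccine.

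The SAP describes the safety tables in two ways.

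- **General statements.** Section 5.2.3 classifies girls for the cumulative summary "after any dose according to the vaccine received at first dose", and its next sentence promises presentation by dengue status: "The safety data will also be presented separately for dengue immune, non-immune / undetermined subjects". Section 5.2.5 adds: "Subjects will be analyzed according to the vaccine they actually received and by baseline dengue status". Section 5.7 says "results for immunogenicity and safety will be presented by baseline dengue status". Protocol section 12.2.3 has the same general promise: "The safety data will also be presented separately for dengue-exposed and dengue unexposed subjects". None of these separates each-dose from any-dose tables.
- **Methods text.** The Safety part of SAP section 5.1.2.2 says: "Safety will be assessed for all subjects and for immune subjects after each and any dose of Cervarix and CYD Dengue vaccine". For the other stratum it says only that "a complementary analysis will be performed for each dose of CYD dengue vaccine, for each and any group, on non-immune subjects". Protocol section 12.1.2.2 likewise plans its split by dengue status for each CYD dose.

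No section limits any-dose summaries to the doses that both strata received, or asks for the number of doses to be shown beside them.

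**The concern.** An any-dose percentage counts a girl once if she has at least one event in any of her collection windows, so it rises with the number of windows. Each injection opens its own window: 7 days for injection site reactions, 14 days for systemic reactions and 28 days for unsolicited AEs. SAP section 4.4.1.3.2 also tabulates SAEs within 28 days of each or any injection. An immune girl who took dose 3 therefore has one more window in which to record an event than a non-immune girl in the same randomised group.

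If the two strata appear side by side in an any-dose table, the non-immune column looks lower even when the risk after each dose is the same. A real excess in non-immune girls would look smaller than it is. The same problem affects a comparison that section 5.1.2.2 does plan, all subjects beside immune subjects, because the all-subjects column mixes girls with two and three CYD doses. Presentation by serostatus was added because the vaccine's profile was found to differ by serostatus, so readers will make these comparisons.

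**Working it through.** **The plan's own safety figure.** The documents give no any-dose rate by serostatus. The only safety figure they state is a 95% probability of seeing an AE of true incidence 1.2% in a group of 240 (SAP section 5.5). This reproduces: 1 - (1 - 0.012)^240 = 0.9448. An incidence of 1.24% gives exactly 95%.

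**Windows per girl** (SAP section 3.1 and Table 3.1)

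- Any CYD dose, either group: 3 for an immune girl with dose 3; 2 for a non-immune girl.
- All injections, Group 1: 3 against 2, because Cervarix shares the visits of CYD doses 1 and 2.
- All injections, Group 2: 5 against 4.

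**Any-dose percentage at equal risk.** With risk p in each window, k windows, and independence between windows, P(at least one event) = 1 - (1 - p)^k. The documents do not give p, so the range below is assumed. Dose 3 uptake among immune girls is taken as complete.

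| p | k = 3 | k = 2 | Gap (points) | k = 5 | k = 4 | Gap (points) |
|---|---|---|---|---|---|---|
| 1% | 3.0% | 2.0% | 1.0 | 4.9% | 3.9% | 1.0 |
| 5% | 14.3% | 9.8% | 4.5 | 22.6% | 18.5% | 4.1 |
| 10% | 27.1% | 19.0% | 8.1 | 41.0% | 34.4% | 6.6 |
| 20% | 48.8% | 36.0% | 12.8 | 67.2% | 59.0% | 8.2 |
| 30% | 65.7% | 51.0% | 14.7 | 83.2% | 76.0% | 7.2 |
| 40% | 78.4% | 64.0% | 14.4 | 92.2% | 87.0% | 5.2 |
| 50% | 87.5% | 75.0% | 12.5 | 96.9% | 93.8% | 3.1 |

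For any CYD dose, the non-immune figure is 67% to 86% of the immune figure with no true difference.

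**Effect on a true difference.** If the per-dose risk were 30% in non-immune girls and 20% in immune girls, any CYD dose would show 51.0% against 48.8%. A 10-point excess per dose would appear as 2.2 points.

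**All subjects beside immune subjects.** Assume half the girls are non-immune, full uptake and p = 30%. The all-subjects figure is 0.5 × 65.7% + 0.5 × 51.0% = 58.4%, against 65.7% for immune girls.

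**Within-girl correlation.** In a beta-binomial model with correlation rho, the 3-against-2 gap at p = 30% is:

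- 12.5 points at rho = 0.1
- 8.9 points at rho = 0.3
- 5.9 points at rho = 0.5
- 2.2 points at rho = 0.8

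It reaches zero only at perfect correlation.

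**Partial uptake.** With half of immune girls taking dose 3 and p = 30% (independent windows), the immune figure is 0.5 × 65.7% + 0.5 × 51.0% = 58.4%. The gap to 51.0% is 7.4 points.

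**With both strata restricted to CYD doses 1 and 2**, each gives 1 - (1 - p)^2: 19.0% at p = 10%, 51.0% at 30%, 75.0% at 50%. The gap is zero throughout.

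**The case against.** The strongest reply is that the non-immune any-dose table may never be produced. The text that sets the non-immune analysis is specific to each CYD dose; its word any refers to group, not dose. Protocol section 12.1.2.2 agrees. This stands. A reader might infer from section 5.2.3 that the side-by-side table is definitely planned, because the sentence on dengue status directly follows the any-dose rule. The general sentences imply it, but the methods text does not name it. The reply does not reach the all-subjects and immune any-dose tables, which section 5.1.2.2 names outright.

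Second, per-dose tables are planned for both strata and are free of the artefact, the withholding of dose 3 is stated openly, and safety is descriptive. A reader might infer that a true excess in non-immune girls would be concealed altogether. It would not: an excess after dose 1 or 2 would show in the per-dose tables. The cumulative tables would still point the wrong way.

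Third, a reader might connect this with the safety finding that led to Amendment 1. That finding concerns hospitalized or severe dengue in the long term, and hospitalized dengue is collected throughout the study, not in post-injection windows. The documents do not support treating this point as masking that risk.

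Fourth, the split of windows is not absolute. Two Group 1 girls had dose 3 before the pause, serostatus not stated (Protocol section 5.1.3), and immune girls who declined dose 3 have two CYD windows.

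Finally, cutting the main all-subjects table down to doses 1 and 2 would depart from the protocol's endpoints, which cover each and any injection. That is a fair limit on the remedy.

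**Conclusion.** The point holds in a limited form. The SAP sections disagree on whether any-dose safety is shown for non-immune girls, and nothing in the SAP makes any-dose percentages comparable where dose counts differ by serostatus. At equal per-dose risk the direction is fixed: the stratum with fewer windows looks lower.

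The size cannot be set from the documents, which give no per-dose rates, serostatus split or dose 3 uptake. Under independence and full uptake, the any-CYD gap runs from about 1 point at 1% risk to about 15 points at 30%. In Group 2 over all injections it runs from about 1 to 8 points. Figures near the top of the range need risks of roughly 20% to 50%, near-complete uptake and little within-girl correlation, so they should not be read as expected values. A lower risk after dose 3 than after earlier doses would also reduce the gap.

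The point covers reactogenicity and AE summaries only. It is a cheap improvement to the tables and does not affect the immunogenicity analyses.

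**What to change.** 1. Reconcile the Safety text of SAP section 5.1.2.2 with sections 5.2.3, 5.2.5 and 5.7, and state whether any-dose safety tables by baseline dengue status are produced.
2. For any such comparison, and for all subjects set beside immune subjects, add an any-dose summary restricted to CYD doses 1-2 and Cervarix doses 1-2, the injections that all girls had received by the pause.
3. Report dose 3 separately, for the girls who received it.
4. Keep the protocol's full any-injection table for all subjects, and show in it the number of doses received.

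The cost is SAP wording, a record selection in existing table programs and one extra labelled table. No new data are needed, and no protocol endpoint is dropped.

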#### **5.2.4 Other Analysis Set**

##### ***Randomized subjects***

A randomized subject is a subject for whom an injection group has been allocated.

## 5.2.5 Populations Used in Analyses

The main immunogenicity analyses (non-inferiority tests) will be performed on the per protocol analyses sets PPX and PPC respectively for Cervarix and CYD dengue vaccine comparisons. The subjects will be analyzed by the vaccine group to which they were randomized.

All other immunogenicity analyses will be performed on the FAS and by baseline dengue status. Subjects will be analyzed by the vaccine group to which they were randomized.

The safety analyses will be performed on the SafAS. Subjects will be analyzed according to the vaccine they actually received and by baseline dengue status.

Complementary analyses on Zika and FV baseline statuses (and by baseline dengue status) will be performed on randomized subjects and on the FAS.

Dengue GMTs by Zika and by FV baseline statuses by Zika baseline status will be performed on all subjects and on FAS dengue immune subjects.

Description of immune response to each dengue serotype according to Zika status at baseline will be performed on FAS dengue immune subjects.

## 5.3 Handling of Missing Data and Outliers

### 5.3.1 Safety

No replacement will be done.

In all subject listings, partial and missing data will be clearly indicated as missing.

#### 5.3.1.1 Immediate

For unsolicited non-serious systemic AEs, a missing response to the “Immediate” field will be assumed to have occurred after the 30-minute surveillance period and will not be imputed.

For SAEs, missing or partially missing elapsed time from last vaccination recorded will remain missing and not be imputed. Such SAEs will not be considered as immediate.

#### 5.3.1.2 Causality

Missing causality (relationship) for unsolicited non-serious AEs and SAEs will be considered at the time of analysis as related to vaccination.

#### 5.3.1.3 Measurements

Partially missing temperatures will be handled as described in Section 4.4.1.1.1.

#### 5.3.1.4 Intensity

For solicited reactions, missing intensities will be handled as described in Section 4.4.1.1.1.

For unsolicited non-serious AEs, missing intensities will remain missing and will not be imputed.

#### **5.3.1.5 Start Date and Stop Date**

Missing or partially missing start dates for unsolicited AEs will remain missing and not be imputed. If either the start or stop date is missing or partially missing, the time of onset will be considered to be missing. Nevertheless unsolicited AEs with missing time of onset will be included in analyses according to the visit collected.

Missing or partially missing stop dates for AEs (solicited reactions and unsolicited AEs) will remain missing and not be imputed.

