##### **4.4.1.2.3 Time of Onset**

Time of onset in days following the vaccination will be computed as follows:

- Time of onset = start date – date of previous vaccination

If the start date of the AE is the same as the last vaccination date, then the onset is “0”.

If one of the dates is partially missing, time of onset will be considered as “Missing”. Events that occur before vaccination (negative time of onset) will not be included in the analyses but will be listed separately. The unsolicited non-serious AEs will be analyzed within 28 days after vaccination, which corresponds to AEs with a time of onset between 0 and 28 days after vaccination or missing. An AE with missing time of onset will be considered to have occurred just after the vaccination indicated by the visit number, so will be included in these tables.

Time of onset will be displayed by period as follows:

- D0-D3
- D4-D7
- D8-D14
- $\geq$  D15
- Missing

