##### 4.4.1.3.2 Time of Onset

Time of onset will be computed using the same methodology as for unsolicited non-serious AEs described in Section 4.4.1.2.3.

SAEs will be analyzed throughout the study using the following periods:

- Within 28 days after each/any injection
- During the study (i.e., all SAEs occurred during the study)

An SAE with missing time of onset will be considered to have occurred after the vaccination indicated by the visit number, so will be included in these tables.

Note: SAEs that occurred before vaccination (negative time of onset) will not be included in analysis, but will be listed separately.

Note for SAEs: Elapsed time from last vaccination recorded will be calculated if the SAE occurred within 24 hours of vaccination.

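### SAP 5.3.1.5 makes onset missing when only the stop date is missing, so a late SAE without a stop date would enter the 28-day SAE tables

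*SAP*

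**What the plan says.** Five parts of the SAP bear on this.

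- **SAP 5.3.1.5 (missing dates):** "If either the start or stop date is missing or partially missing, the time of onset will be considered to be missing". It continues: "Nevertheless unsolicited AEs with missing time of onset will be included in analyses according to the visit collected". Stop dates that are missing or partial are left as they are.
- **SAP 4.4.1.2.3 (onset, unsolicited non-serious AEs):** "Time of onset = start date – date of previous vaccination". The 28-day analysis takes in events "which corresponds to AEs with a time of onset between 0 and 28 days after vaccination or missing". It also says: "An AE with missing time of onset will be considered to have occurred just after the vaccination indicated by the visit number".
- **SAP 4.4.1.3.2 (onset, SAEs):** "Time of onset will be computed using the same methodology as for unsolicited non-serious AEs described in Section 4.4.1.2.3". It names two reporting periods, "Within 28 days after each/any injection" and the whole study. It then says: "An SAE with missing time of onset will be considered to have occurred after the vaccination indicated by the visit number", and that such SAEs go into the tables.
- **SAP 4.4.1.4.2 and 4.4.1.4.3:** seriousness and outcome are tabulated for all and for related SAEs in the 28-day period.
- **SAP 4.4.1.2.4 (duration):** duration is missing if either date is blank or missing, or if the ongoing box is ticked.

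Three points in the protocol give the context. A footnote in 9.2.2.3.3 treats an AE with no stop date as ongoing at the end of the trial. Section 9.2.2.3.4 has SAEs collected until six months after the last vaccination. The definitions in 9.2.2.1 make SAEs a subset of unsolicited AEs, so the wording of SAP 5.3.1.5 reaches them.

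**The concern.** When an event began does not depend on whether or when it ended. SAP 4.4.1.2.3 respects that; SAP 5.3.1.5 does not. Under 5.3.1.5 a complete start date is set aside because a different date is absent, and the event is then handled as if its timing were unknown.

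Counting events of truly unknown onset in the 28-day window is a reasonable conservative convention. Applied to an event whose start is known to be after Day 28, it puts that event in a table where it does not belong. Because the trigger is a missing stop date, the events moved would tend to be unresolved ones, so the outcome table could shift as well as the count. Two programmers could each follow the SAP and produce different 28-day SAE tables from the same data.

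**Working it through.** The plan gives no figure to reproduce, since this is a derivation rule. The check applies both rules to the same records.

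**Inputs.** Vaccination is on Day 0.
- Rule A (SAP 4.4.1.2.3): onset = start − vaccination date, missing only if one of those two dates is missing.
- Rule B (SAP 5.3.1.5): onset is missing if the start or the stop date is missing; otherwise start − vaccination date.
- 28-day filter (SAP 4.4.1.2.3, carried to SAEs by 4.4.1.3.2): count the event if onset is 0 to 28 or missing.

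| Start | Stop | Onset, A | In 28-day table, A | Onset, B | In 28-day table, B |
|---|---|---|---|---|---|
| D10 | D20 | 10 | yes | 10 | yes |
| D10 | none | 10 | yes | missing | yes |
| D35 | none | 35 | no | missing | **yes** |
| D60 | none | 60 | no | missing | **yes** |
| D120 | none | 120 | no | missing | **yes** |
| D120 | D130 | 120 | no | 120 | no |
| none | none | missing | yes | missing | yes |

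Three things follow.

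1. The rules differ in table membership only for a known start after Day 28 with no stop date.
2. Under B, the two D120 rows are classified differently solely because one has a stop date.
3. An event starting on D10 with no stop date is counted either way, but under B it moves from the D8–D14 onset category to Missing.

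**Which events can reach the bold rows.** Non-serious unsolicited AEs are collected for Days 0–28 after each injection, so late starts among them should be few. SAEs are collected throughout and can start well after Day 28.

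**How much SAE follow-up lies outside the windows.** This is an illustration only. Assumptions: the planned schedule, months of 30.44 days, and a subject who receives all doses.
- Group 1: three vaccination dates, 3 × 29 = 87 window days out of 549; 1 − 87/549 = 84% outside.
- Group 2: each Cervarix dose and the CYD dose 28 days later have windows sharing one day, so 2 × 57 + 29 = 143 window days out of 577; 1 − 143/577 = 75% outside.
- With a 6-month pause added before the third CYD dose: 1 − 87/731 = 88% in Group 1 and 1 − 143/759 = 81% in Group 2.

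These are shares of follow-up days, not of events. They show that late-starting SAEs are possible over most of the follow-up, and no more than that.

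**The case against.** The best case for leaving the text alone has four parts.

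**Ongoing is not the same as missing.** SAP 4.4.1.2.4 lists a ticked ongoing box separately from blank or missing dates, while 5.3.1.5 speaks only of missing or partial dates. A programmer could exempt ticked-ongoing events. The protocol footnote that equates no stop date with ongoing describes status at trial end and sits in the section on non-serious AEs. This part stands as a limit: a reader might infer that every ongoing SAE loses its onset, and the text does not settle that. But 5.3.1.5 writes no exemption, and an SAE whose stop date is simply missing is caught on any reading.

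**The SAE wording is looser.** SAP 4.4.1.3.2 places a missing-onset SAE after the vaccination, not just after it as in 4.4.1.2.3, and names two periods before referring to the tables. Inclusion in the 28-day table is therefore an inference. It is the natural one, since the section adopts the method of 4.4.1.2.3, whose 28-day definition admits missing onset.

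**The consequence is modest.** Safety is descriptive. The protocol's SAE endpoint covers the whole trial, and that table counts the same post-vaccination SAEs under either rule. SAEs are also listed individually. The error adds events to the window and hides none. Causality is judged by the investigator and the sponsor, not by the window, so the inference that misplaced events would become vaccine-related is not supported. All of this stands.

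**Few events may be affected.** Stop dates of related AEs are actively sought, and unresolved related events are followed up. This also stands, although unrelated SAEs have no equivalent provision for stop dates.

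**Conclusion.** The contradiction is real and lies in the SAP's own text. SAP 5.3.1.5 makes onset depend on the stop date; 4.4.1.2.3 does not. Read with 4.4.1.3.2, the rule in 5.3.1.5 would put an SAE with a complete start date after Day 28 and no stop date into the 28-day SAE tables, including seriousness and outcome, and leave out the same SAE once it has a stop date.

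The size is limited. Only descriptive safety tables are touched; no hypothesis test, alpha or power is involved. The 28-day table of non-serious unsolicited AEs would hardly change in its counts, though some events would lose their onset category. The number of affected SAEs cannot be derived from the documents.

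A reader might go further and estimate that most ongoing SAEs would be misplaced, for example 1 − 29/182 = 84% over a six-month interval or 1 − 29/365 = 92% over a twelve-month gap. The documents do not support this. It assumes uniform onset and applies to an unknown number of events. The longer gap arises only for seropositive subjects who go on to the third CYD dose, and in Group 2 a CYD dose follows each Cervarix dose by about 28 days. Nor do the different follow-up shares in the two groups show a bias between them.

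The conclusion rests on two readings: that 5.3.1.5 applies to SAEs, as the protocol's definitions indicate, and that missing-onset SAEs enter both SAE periods.

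**What to change.** In SAP 5.3.1.5, replace *start or stop date* with *start date*, and state that onset is missing only when the start date or the date of the previous vaccination is missing or partial. Keep the missing-stop-date and ongoing rule for duration only, where SAP 4.4.1.2.4 already has it.

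With this change the D35, D60 and D120 events without a stop date have onsets of 35, 60 and 120 and leave the 28-day tables. The D10 event stays in and keeps its onset category. An event with no start date is still counted, so the conservative convention for truly unknown onset is preserved.

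The cost is one SAP sentence and no new data. If the onset derivation has already been programmed, it should be checked against the corrected sentence.
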